6 OBJECTIVES AND OUTCOME MEASURES

Objectives	Outcome Measures	Timepoint(s) of evaluation of this outcome measure (if applicable)
Primary		
To test whether a digital platform can efficiently identify patients who have suffered a bleeding event and	At least 200 patients correctly identified as having suffered bleeding, of which 40 (20%) provide consent	End of study

are willing to consent for the routine blood samples to be used in research.
		

Secondary
		

 1. To conduct a Delphi process with an expert panel to identify criteria that could be applied in the electronic patient record to identify patients with acquired bleeding 2. To use 10 years’ of retrospective data to map bleeding criteria to appropriate data fields within the electronic patient record data sources 3. To encode bleeding criteria into a real-time “algorithm” and display results within a digital web-based platform 4. To measure and refine the accuracy of the algorithm, by manual review of free-text notes of patients identified as bleeding 5. Assess the feasibility of sample sequestering by the lab 6. Assess the feasibility of performing blood clotting and endothelial factor analysis on the sequestered samples. 	
 1. List of bleeding criteria 2. Bleeding criteria mapped to appropriate data fields on the electronic patient record 3. Digital platform capable of identifying bleeding patients in real-time 4. Algorithm accuracy before/after refinement 5. List of unique challenges faced by the laboratory team during blood sample retention and analysis 6. Numbers of samples retained and additional blood clotting and endothelial factor results captured from the retained samples. 	
End of study

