9 PROTOCOL PROCEDURES

9.1 Algorithm development and validation

- Conduct a modified Delphi process using a panel of clinical experts to identify a set of starting criteria (algorithm) e.g. transfusion request or absolute/drop in Hb. In the first instance, we will aim to agree broad criteria that maximise the sensitivity of the algorithm.
- The Clinical Data Warehouse (CDW) is a digital resource within the Oxford University Hospitals NHS Trust (OUH) that will provide up to 10 years of retrospective anonymised patient data to the study. This dataset will comprise demographics and diagnostic/therapeutic codes, hospital locations, admission/discharge timings as well as laboratory results, radiology reports, blood product usage and operative management and outcomes. All data will be time-stamped.
- Using this retrospective patient data, we will develop an algorithm by mapping criteria identified by the Delphi process to routinely-collected data sources. We will combine these mapped criteria into a single algorithm to identify bleeding patients. We will assess its sensitivity to identify patients who have received treatments/investigations for bleeding (e.g. urgent endoscopy, prescription of tranexamic acid, blood transfusions). We will calculate basic demographics (e.g. age, mortality rates) for the patient cohort and compare these to previously published data e.g. from the Trauma Audit Network (TARN) audit. We will also look at how individual criteria overlap to see whether we can identify any redundancy in the list of data sources.
- Sources of patient data required by the algorithm will be integrated into a “real-time” digital platform by processing HL-7 messaging from individual hospital IT systems. This will expand on a pre-existing software platform (developed for the HAVEN Study, <https://ora.ox.ac.uk/objects/uuid:322561c7-866e-4c1e-bcc1-65da4da477fb>) which listens to hospital wide computer systems, integrating relevant data into a real-time research database.
- Using the real-time database, we will implement the algorithm on a lightweight web interface (R Shiny). The interface will include the ability for users to input additional data from the notes review (details below).

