- Research nurses will use the interface to identify (up to 200) patients who are potentially bleeding and review their free-text notes in the electronic patient record, notifying attending clinicians when there is no documentation of bleeding. Using the additional clinical information in patients’ notes, the nurses will record whether they agree with the output of the algorithm. Where the algorithm has incorrectly identified patients as having bled, the nurses will record the reasons for bleeding based on the clinical information in the notes.
- The expert panel will review the results of the notes review and refine the algorithm to increase its specificity.
- The expert panel will not have any access to confidential patient information.

9.2 Consent patients identified by system for use of surplus routine blood samples in research analysis.

In the final three months of the study, we will prospectively test the accuracy of the algorithm and the feasibility of using the real-time platform for consenting patients to use their data and routine blood samples for future research.

When the algorithm identifies that a patient has met the criteria for bleeding, the platform will:

- Allocate the patient a RE-BLEED study ID.

- Electronic Hospital Record (EHR) data for this entire encounter will be retained in the study database and when the encounter ends the record will be pseudo-anonymised.
- A notification will be sent to the main hospital laboratory requesting that their (left-over) blood samples, once all clinical testing has been completed as part of routine clinical care, be retained for use in the study, pending patient consent. Where consent is not given, the samples will be destroyed as per local protocols.

In order to be able to screen all patients in the hospital, the system must collect data for all adult patients from their admission to their discharge. The records of adult patients admitted to the hospital who do not meet the eligibility at any point during their admission will be destroyed at the point they are discharged from hospital.

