11.2.2 Prospective data

Up to 87,500 records will be screened by the digital platform to identify those who may have bled over 2 three-month periods.

In the first three-month period, research nurses will review electronic records of patients with bleeding (identified by the algorithm), we estimate around 250 will experience a bleeding event. Assuming the algorithm has a sensitivity of 80%, we plan to review 200 electronic records.

In the second three-month prospective period, research nurses will approach patients for consent. Based on the assumption that 200 patients will also be identified by the algorithm in this period, we will aim for at least 40 (20%) of patients to consent to their participation.

We will assess the efficacy of the sample retention process being used by the study. This will include the number of samples successfully retained, the number of additional clotting laboratory resulted gained from these samples and any feedback from the laboratory staff regarding challenges they faced.

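### The before/after accuracy outcome reviews flagged patients only, so it measures PPV, and no sensitivity check is stated after the algorithm is narrowed

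*Protocol*

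**What the plan says.** Protocol section 6 (also the synopsis) gives secondary objective 4 as "To measure and refine the accuracy of the algorithm, by manual review of free-text notes of patients identified as bleeding". The matching outcome is accuracy before and after refinement, with no component of accuracy named.

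Section 9.1 sets the order of work:
- The Delphi panel begins wide: "In the first instance, we will aim to agree broad criteria that maximise the sensitivity of the algorithm".
- The criteria are mapped to retrospective data, where sensitivity is assessed: "We will assess its sensitivity to identify patients who have received treatments/investigations for bleeding (e.g. urgent endoscopy, prescription of tranexamic acid, blood transfusions").
- Nurses then review the notes of up to 200 patients whom the interface shows as potentially bleeding.
- After that review, "The expert panel will review the results of the notes review and refine the algorithm to increase its specificity".

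Section 9.2 adds a later check: "In the final three months of the study, we will prospectively test the accuracy of the algorithm". It names no component of accuracy and no review of unflagged patients. It also says that the records of adult patients "who do not meet the eligibility at any point during their admission will be destroyed at the point they are discharged from hospital".

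Section 11.2.2 estimates about 250 bleeding events in the first three-month period and continues: "Assuming the algorithm has a sensitivity of 80%, we plan to review 200 electronic records". It assumes that 200 patients are again identified in the second period.

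**The concern.** The protocol sets up a trade-off and then, after refinement, looks directly at one side of it. Broad criteria are chosen so that few bleeders are missed, and the panel then narrows them to remove false positives. Narrowing can also remove true bleeders. A sample made up only of flagged patients contains no missed bleeders, so it cannot show that loss. The one stage where missed bleeders could be counted, the retrospective assessment, is described only for the algorithm as it stood before narrowing.

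At stake is how secondary outcome 4 is read. The platform is meant to find bleeding patients across a whole hospital for later trials (section 5, Aim). A reported gain in accuracy that does not show how many bleeders the refined version no longer finds would be a poor guide to that use.

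**Working it through.** **1. The plan's own figures.** Section 11.2.2: 250 × 0.80 = 200, which reproduces. This 200 is the expected number of true positives. It equals the number of flagged records only if there are no false positives (PPV 100%). Records screened: 175,000 / 2 = 87,500, which also reproduces. An equal split (assumed) gives 43,750 per three-month period, hence 43,750 − 250 = 43,500 non-bleeders.

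**2. What review of flagged patients can estimate.**
- PPV = TP / (TP + FP). Both terms are observed.
- Sensitivity = TP / (TP + FN). FN lies wholly among unflagged patients and is not observed.
- Specificity = 1 − FP / non-bleeders. It can be approximated if screened and flagged counts are kept and every flagged patient is reviewed.

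With 160 true and 40 false positives, PPV is 80% and specificity about 99.91% whatever FN is. If FN is 0, 40, 160 or 640, sensitivity is 100%, 80%, 50% or 20%.

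**3. How refinement can hide a loss.** Assume 200 flagged, all reviewed, and a starting PPV of 50%. Starting specificity is 1 − 100/43,500 = 99.77%.

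| After refinement (TP + FP) | PPV | Specificity | Confirmed bleeders lost |
|---|---|---|---|
| 100 + 50 | 100/150 = 66.7% | 1 − 50/43,500 = 99.89% | 0% |
| 80 + 40 | 80/120 = 66.7% | 1 − 40/43,500 = 99.91% | 20% |
| 60 + 30 | 60/90 = 66.7% | 1 − 30/43,500 = 99.93% | 40% |

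PPV does not separate the three cases, and specificity looks slightly better as more bleeders are lost. The same scaling from 40 + 160 gives a PPV of 33.3% throughout, and from 160 + 40 it gives 88.9% throughout. The 50% case implies 100/250 = 40% sensitivity against the protocol's estimate of 250 bleeds, so it illustrates the mechanism and is not a forecast.

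**4. The second-period count as a check.** If the refined algorithm loses 20% or 40% of the bleeders previously found, the expected 200 falls to 160 or 120. But 160 found is 160/250 = 64% sensitivity if there were 250 bleeds, and 160/200 = 80% if there were 200. The count cannot separate lost sensitivity from fewer bleeds.

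**5. Precision of PPV.** Exact 95% intervals for 200 reviewed: 40/200, 14.7% to 26.2%; 100/200, 42.9% to 57.1%; 160/200, 73.8% to 85.3%. PPV is adequately measured. The gap is sensitivity.

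**6. Where the loss could be measured.**
- Random review of unflagged prospective records yields too little. With 50 missed among 43,750 − 200 = 43,550 unflagged, 200 records would contain 200 × 50/43,550 = 0.2 missed bleeders. With 40 of 250 found, the figure is 200 × 210/43,550 = 1.0.
- The retrospective data give enough. The protocol's rate implies 250 × 4 × 10 = 10,000 bleeders in ten years. Assume 1,000, 5,000 or 10,000 were treated or investigated, that sensitivity falls from 80% to 72%, and that refinement only removes flags. The retained share is then 720/800, 3,600/4,000 or 7,200/8,000, each 90%, with exact 95% intervals of 87.7% to 92.0%, 89.0% to 90.9% and 89.3% to 90.6%.
- First-period confirmed bleeders still flagged, if 90% are kept: 36/40, 76.3% to 97.2%; 90/100, 82.4% to 95.1%; 144/160, 84.3% to 94.2%.

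**The case against.** The strongest reply is that this belongs in the SAP, which section 11 says will be finalised before any analysis. The remedies are analytic, the retrospective data are kept, and nothing in the protocol prevents a rerun. That lowers the urgency. It does not remove the point, because the protocol itself fixes who is reviewed, what refinement aims at and when sensitivity is assessed.

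A second reply is that the count of correctly identified patients would fall if many bleeders were lost. This stands in part, as a crude check that rests on the estimate of 250 bleeds.

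A third is that this is one secondary outcome of a feasibility study with no decision points (section 11.4). That limits the stakes, although algorithm accuracy is a stated aim in section 5.

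Three stronger readings are tempting and are not supported:
- *The retrospective sensitivity is circular.* A reader may note that the panel is to "identify a set of starting criteria (algorithm) e.g. transfusion request or absolute/drop in Hb" while blood transfusion is among the reference treatments. Both are examples, and the Delphi criteria are not yet set. The stated target is treated or investigated bleeding, and against that target overlap is not clearly a bias.
- *Specificity is the wrong target.* Removing false positives does raise specificity, and it can be approximated. Renaming the target PPV would not reveal lost bleeders either, as the table shows.
- *Unflagged prospective records must be kept and sampled.* A random sample of practical size would find almost no missed bleeders.

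**Conclusion.** The point holds. As written, secondary outcome 4 directly yields PPV and not sensitivity, and no sensitivity assessment is stated after refinement. An apparent improvement is compatible with losing anywhere from none to 40% of confirmed bleeders in the scenarios shown. Those scenarios rest on an assumed PPV and assumed proportional losses. They show that a loss could go unseen, not that one will occur. The document gives no basis for predicting its size. PPV itself is well estimated from 200 records. This is a worthwhile, low-cost improvement to one secondary outcome and not a flaw that undermines the study.

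**What to change.** 1. Report the prospective notes review as PPV with an exact confidence interval, and take the refined algorithm's PPV from the second three-month period.
2. Run the starting and refined algorithms on the same retrospective admissions, against the same treatment/investigation reference, and report the paired change in sensitivity. Section 11.1.1 extracts the same variables for both cohorts, and section 11.2.1 holds up to 1,750,000 admissions, including unflagged ones.
3. Report the share of first-period confirmed bleeders still flagged after refinement, with an exact interval. Label it as optimistic, because refinement used those records, and as blind to bleeders missed by both versions.
4. Optional: if the final Delphi criteria include a reference treatment or its request, add an analysis with those criteria removed, alongside and not in place of the sensitivity of the deployed algorithm.

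The cost is wording and a little more analysis. The rerun needs refined criteria that map to retrospective fields, and it covers treated or investigated bleeding only. It may somewhat overstate the loss, because the starting algorithm was developed on those same data.

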9.3 Blood sample handling /temporary storage and testing

Following notification by the electronic identification process, left-over EDTA and citrate blood samples from potentially eligible patients (which were taken as part of normal clinical care) will be transferred to a dedicated `holding area` in the MRC Weatherall Institute of Molecular Medicine (WIMM).

Prior to consent being sought, all sequestered left-over samples will undergo processing to extend their viability for later analysis. This will occur in the holding area. The processing will consist of:

- Citrate samples will be spun down and the plasma and buffy coat will be aliquoted off into separate tubes
- Any remaining serum from a sample will also be aliquoted off

Samples will be processed, frozen and retained by the WIMM (The MRC Weatherall Institute of Molecular Medicine) laboratory in a dedicated area allocated to only this study. The samples will be labelled with the study ID number. Samples will be held (without consent) for a total of 28 days from the time they were taken, to maximise the time and opportunity for the study team to formally consent patients for use of these samples in the study.

Members of the study team will liaise with the clinical care team who will approach the patient and if appropriate introduce the trained study team member. The study team member will then explain the purpose of the study and seek the patient's consent. If consent is obtained, the laboratory will be notified that the sample can be retained until the end of the study. If the patient does not consent, the laboratory will be notified to destroy the sample in line with local policies.

If written consent has not been obtained after 28 days from the bleeding episode all samples will be destroyed in line with local policies.

Where consent is provided, plasma samples will be analysed for haemostatic potential using:

- Standard clotting analysis: Prothrombin time (PT) and activated partial thromboplastin time (APTT) (if not already performed as part of the clinical care), clot lysis, thrombin generation, clotting factor levels and the contributing role of platelet factors.
- Fibrinogen concentration

- Endothelial cell markers: Thrombomodulin & syndecan-1

Where possible the tests will be performed on the EDTA and citrate samples to maximise the yield (e.g. endothelial markers). Tests such as those that assess the contributing role of platelet factors, can only be performed on the buffy coat aliquots.

Samples will be destroyed in keeping with standard laboratory practice at the end of the study period (unless the patient has provided specific written consent for their samples to be used in future ethically approved research). The results of these tests will be added to the digital study record. An anonymous version of this data may be used by future studies and this mentioned specifically on the consent form.

We do not expect the results to be relevant to current or future treatment. However, if an unexpected finding is reported, such as an abnormally low level of a clotting factor, the research team will invite the participant for review by a senior clinician within the Oxford Haemophilia and Thrombosis Centre.

9.4 Consent & patient notification

This applies to the prospective part of the study.

9.4.1 Screening/enrolment

Permission to screen all patients in the hospital by digitally accessing their confidential health records and will be sought from the Confidentiality Advisory Group (CAG). The justification for requiring access to health records without explicit consent is that patients must be identified very rapidly, and at a hospital wide scale, making this not practicable to obtain informed consent.

9.4.2 Dissent

Screening for eligibility will occur digitally and the NHS Opt out will be used as a marker of prior patient dissent. Patients who have completed the NHS Opt out will be removed from the screening process and all associated data will be destroyed.

Contact details for study specific dissent / withdrawal will present on the study website, patient information sheet and patient facing materials such as posters etc. Contact details for the study team / office will be present on these documents and anyone contacting the study team will be able to request for their records to be removed from the study without any effects on their care.

9.4.3 Patients with capacity to consent

Formal written consent will be sought from a subset of patients to analyse surplus clinical blood samples. This will be conducted by group of experienced research nurses.

Patients with the physical and mental capacity to give informed consent will be approached in person during the first 28 days following their episode of bleeding and it will be explained to the patient that they have already had blood samples sent for storage. It will be made clear that these samples have not yet been analysed and that these samples will be destroyed if they do not agree to the samples being used.

For any patient where a sample was retained with the intent to be used in the study but the patient did not regain capacity within 28 days, information will be provided to either a personal or a professional consultee for advice about the research use of the sample (see next section).

After this period has past, if consent has not been obtained, all samples will be destroyed.

Patients or their personal or professional consultee will be provided with:

- RE-BLEED patient information leaflet
- RE-BLEED consent form

The RE-BLEED study documentation will detail no less than: the nature of the study; what it will involve for the participant; the implications and constraints of the protocol; the known side effects and any risks involved in taking part. It will be clearly stated that the participant is free to withdraw from the study at any time for any reason without prejudice to future care, without affecting their legal rights, and with no obligation to give the reason for withdrawal.

The participant or consultee will personally sign and date the latest approved version of the Informed Consent form or Consultee Declaration.

The participant, or their consultee, will be allowed a maximum of 28 days to consider the information, and the opportunity to question the Investigator, their GP, or other independent parties to decide whether they will participate in the study.

Written Informed Consent will then be obtained by means of participant-dated signature (or consultee dated signature) and dated signature of the person who presented and obtained the Informed Consent/Consultee Declaration. The person who obtained the consent will be suitably trained and will have been authorised to do so by the Chief Investigator. A copy of the signed Informed Consent/Consultee declaration will be given to the participant. A copy will be added to the medical notes. The original signed form will be retained at the study site.

[figure not shown]

Figure 1 - Consent flow chart

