Understanding variation in patients’ response to treatments for bleeding requires large studies. This study aims to develop a real-time digital platform, whereby bleeding patients among the whole hospital population can be efficiently identified by an algorithm and approached for their consent to participate in research studies. The platform will also integrate multiple sources of patient data, from which study data sets can be automatically created. In this feasibility study, we will assess the accuracy of the algorithm for identifying bleeding patients and whether a significant proportion (25%) of these patients are willing to consent for their data and routine blood samples to be used for research. Once developed, the digital platform could be deployed across multiple sites to facilitate efficient identification of potential participants for future clinical trials.

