9.4.4 Patients without capacity to consent

Patients who experience an episode of bleeding may transiently experience a lack of capacity to consent, either due to the bleeding itself or the resulting treatment. Bleeding also occurs in those who already lack capacity or in patients who may lose capacity as a result of the event (i.e. trauma with brain injury).

This is a feasibility study trialling a consent model designed to be used in a subsequent interventional trial, of patients during a bleeding episode. A future trial would include randomisation to an intervention, as well as sequestering all available blood samples. Our consent model must be able to include those who lack capacity at the time of bleeding in order to be able to offer an effective future intervention. It is essential that any future study does not exclude those who either had a temporary or permanent lack of capacity, as this would both introduce bias into the study but also deprive the most vulnerable and severely affected from a chance to participate in a study.

Capacity to consent to this study, will be assessed by the clinical team looking after the patient and confirmed by members of the study team. For patients lacking capacity, a personal or professional consultee will be approached.

If a personal consultee is not available, a professional consultee will be consulted. For the purpose of this study, a professional consultee is defined as a clinician (qualified doctor or registered nurse) with

appropriate training (according to local Trust policies) to take on the role of professional consultee. Professional consultees must not be directly involved in the patient's care and cannot be a member of the core study team at site.

If a consultee declines to give consent/advice for the samples and any associated sample data to be retained in the study at any stage, his/her wishes will be respected. A consultee is free to withdraw their support for continuation in the study at any time.

Participants where a consultee has been sought will be visited regularly during their admission, including just prior to discharge. If capacity is regained at any point, then informed consent will be sought. If the patient chooses not to provide consent data and samples will be destroyed. If capacity is not regained, then the samples and data will be included in the planned analysis.

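### The 40-of-200 consent measure is a recruitment yield, so on its own it cannot show whether patients are willing to consent

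*Protocol*

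**What the plan says.** **The question.** The primary objective in Section 6 concerns patients who have bled and "are willing to consent for the routine blood samples to be used in research". The Aim in Section 5 asks "whether a significant proportion (25%) of these patients are willing to consent".

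**The measure.** Section 6 gives one outcome for this objective: "At least 200 patients correctly identified as having suffered bleeding, of which 40 (20%) provide consent". Section 11.2.2 sets the same target for the second three-month period: "Based on the assumption that 200 patients will also be identified by the algorithm in this period", and then "we will aim for at least 40 (20%) of patients to consent to their participation".

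**Who is asked.** Three statements do not fit together without explanation:
- Section 9.4.3: "Formal written consent will be sought from a subset of patients to analyse surplus clinical blood samples".
- Section 9.5: once identified, the cohort is approached for consent, with no sub-selection mentioned.
- Section 12.3: some patients are not approached and contribute anonymised data only.

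**Who may sign.** Section 9.4.4 says "For patients lacking capacity, a personal or professional consultee will be approached". Section 9.4.3 lists a consultee's dated signature beside the participant's as a way of obtaining written informed consent, although it names the consultee declaration as a separate form. Under Section 9.4.4, samples and data from consultee-supported patients stay in the analysis if capacity is not regained. Section 9.6 expects most, possibly all, of the intended participants to lack capacity at presentation.

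**Time limit.** Under Sections 9.3 and 9.4.3, samples are destroyed if consent has not been obtained within 28 days.

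**The concern.** Willingness is a property of people who have been asked. A ratio of consents to patients identified is the product of two things: the share reached, and the share of those reached who agree. A patient who goes home, dies or is not found within 28 days stays in the denominator exactly as a patient who declines does.

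The distinction matters because Section 9.4.4 presents the study as a trial run of a consent model for a later interventional trial. A low figure caused by refusals would point to the consent model. A low figure caused by patients not being reached would point to staffing or timing. A single ratio over all identified patients cannot tell these apart.

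The numerator has a related gap. If consultee declarations count towards the 40, part of the figure reflects the judgement of someone other than the patient. The protocol does not say whether they count.

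**Working it through.** **1. The plan's own figures.** Section 11.2.2 states "we estimate around 250 will experience a bleeding event. Assuming the algorithm has a sensitivity of 80%, we plan to review 200 electronic records". 250 × 0.80 = 200, and 200 × 0.20 = 40. Both reproduce, so this is not an arithmetic error. No power calculation is stated, so there is none to reproduce.

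**2. What the ratio contains.** Let *f* be the share of the 200 who are approached and *w* the share of those approached who agree. Then

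yield = *f* × *w*, so *w* = 40 / (200 × *f*).

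The protocol gives no value for *f*.

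**3. Agreement rates compatible with 40 consents.** Intervals are exact (Clopper-Pearson), the method Section 11.1.2 names for proportions: lower limit = Beta quantile 0.025 (x, n − x + 1), upper limit = Beta quantile 0.975 (x + 1, n − x), with x = 40. The numbers approached are assumptions.

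| Approached (assumed) | Agreement | Exact 95% CI |
|---|---|---|
| 200 | 20.0% | 14.7 to 26.2 |
| 160 | 25.0% | 18.5 to 32.4 |
| 100 | 40.0% | 30.3 to 50.3 |
| 80 | 50.0% | 38.6 to 61.4 |
| 50 | 80.0% | 66.3 to 90.0 |

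**4. How far reach alone decides whether the target is met.** Assume true willingness of 50% and treat each of the 200 as consenting independently with probability *f* × 0.5. The chance of at least 40 consents is the upper binomial tail with n = 200:
- *f* = 30%: p = 0.15, chance 0.03.
- *f* = 40%: p = 0.20, chance 0.53.
- *f* = 60%: p = 0.30, chance above 0.99.

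Willingness is the same in all three lines. Only reach changes.

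**5. If consultee declarations were counted.** The share is unknown and is assumed here, with 200 kept as the denominator:
- A quarter of the 40: patients' own consents are 30/200 = 15.0% (10.4 to 20.7).
- Half of the 40: 20/200 = 10.0% (6.2 to 15.0).

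**The case against.** **Consents per identified patient is the right feasibility measure.** The objective is about what the platform can deliver, and a later trial would also lose the patients it cannot reach. This stands: 40/200 is a legitimate yield and should be kept. It does not supply the willingness conclusion that the objective and the Aim also ask for.

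**A reader might infer that only some of the 200 are approached.** The documents do not establish this. The prospective part screens up to 87,500 records, and consent is sought only in the last three months. The subset in Section 9.4.3 may therefore mean simply the flagged patients of that period. Section 9.5 reads that way, and the patients not approached in Section 12.3 could be those of the first period. What stands is that the sections are not reconciled. The main point does not depend on the answer, because even if all 200 are meant to be approached, some may not be reached within 28 days.

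**A reader might infer that consultee declarations are counted in the 40.** No section says so. The outcome speaks of patients providing consent, and the retention rule in Section 9.4.4 concerns samples and data. Counting them could also be deliberate, since the consent model is meant to include people without capacity. The matter is open, which is a reason to state the rule and report the two routes separately.

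**A reader might infer that unreached patients are classed as unwilling.** The protocol counts them only as not having consented. The error would arise if that count were read as willingness.

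**This is detail for the statistical analysis plan.** Section 11 promises such a plan, which is not at hand, and reasons for non-approach could sit there. But the protocol itself fixes the primary measure and its denominator, and the unreconciled statements are in the protocol.

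**Conclusion.** The point holds as one of definition. The 40/200 measure is a recruitment yield, reach multiplied by agreement, and cannot by itself support a conclusion on whether patients are willing to consent. In addition, Sections 9.4.3, 9.5 and 12.3 disagree or are unclear on who is asked, and the status of consultee declarations in the numerator is not stated.

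The possible distortion is large but not fixed by the documents. The same 40 consents are compatible with agreement from 20%, if all 200 are approached, up to 100%, if only 40 are. Every value below 200 approached, and every consultee share, is an assumption used for illustration. If all 200 were in fact approached and all 40 signatures were the patients' own, yield and willingness would coincide.

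This is a cheap improvement. It leaves the target and the design unchanged.

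**What to change.** 1. Keep 40/200 and label it recruitment yield.
2. State whether a consultee declaration counts towards the 40.
3. Reconcile Sections 9.4.3, 9.5 and 12.3 so that it is clear which patients are to be approached.
4. Add two proportions, each with the exact 95% interval already named in Section 11.1.2:
   - patient consents over patients with capacity actually approached;
   - consultee agreements over consultees approached.
5. Report the number not approached by reason, for example died, discharged, no nurse available, or not reached within 28 days.
6. Draw the willingness conclusion from the rate among patients approached, not from the yield.

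**Cost.** The nurses need to keep an approach log. Section 9.1 already plans for users to enter additional data from the notes review in the interface, so the log could be added there. The report would carry more than one headline figure. The rate among patients with capacity does not describe those without capacity, which is why the consultee proportion should appear beside it.
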